### **10.1.4 SAFETY DATA**

A total of 448 subjects have been exposed to reparixin in the clinical studies completed to date, of whom 337 and 112 received i.v. formulation and oral tablets, respectively. The patient population exposed to i.v. formulation includes 103 adult healthy subjects (100M/3F), 17 patients with different grades of renal impairment (12M/5F), 16 patients undergoing cardiopulmonary by pass (10M/6F), 46 patients undergoing lung transplantation (23M/23F), 48 patients undergoing kidney transplant (31M/17F), 22 undergoing liver transplant (18M/4F) and 85 receiving intrahepatic pancreatic islet infusion (32M/53F), with 22 patients in this group receiving reparixin twice. Exposure included short or prolonged i.v. infusion up to 10.6 mg/kg over 30min or 133 mg/kg over 48h and, in pancreatic islet and liver transplantation studies, 2.772 mg/kg body weight/hour i.v. continuous infusion for 7 days. Overall, reparixin was safe and well tolerated in both healthy subjects and critically ill patients. In phase 1 studies, no deaths, Serious Adverse Events (SAEs) or Adverse Event (AE)-related withdrawals were reported. The majority of AEs reported were of mild intensity. All subjects had recovered completely or had ongoing adverse events of mild intensity when they were discharged. The safety of reparixin was confirmed also in patients with different grades of renal impairment. In the interaction study no safety concerns were raised during co-administration of midazolam/tolbutamide with reparixin. During phase 2 and 3 studies, AE and SAE profile was similar for both placebo and reparixin groups and no particular safety concerns were raised. Data obtained in the trials in islet transplantation further support the safety profile of the proposed dose, even after a 7 day administration, repeated twice in several patients. Most frequent ADRs were nausea, headache, and vomiting; great majority of these were mild to moderate in nature and none required discontinuation of the Investigational Product. Tachycardia occurred in one patient from Days 5 to 38 after 1st islet infusion was judjed probable in relation to Investigational Product. Vomiting, nausea and headache on Day 5 and 6 after 2nd islet infusion in one patient and erythema, nausea and headache on Days 2 to 6 after 1st islet infusion in another patient were judged highly probable in relation to the Investigational Product. Nausea, vomiting and severe gastrointestinal bleeding associated with anaemia developed in a female patient early after the beginning of reparixin infusion because the patient received a dose of reparixin 3 times as high as that foreseen in the protocol (medical error). These events were assessed as serious by the investigator and by the Sponsor.

Overall, the most frequent (>10%) ADRs observed in the phase 1 to phase 3 I.V. studies were: Gastrointestinal disorders (about 26% of the total number of reports), including abdominal pain lower, abdominal pain NOS, abdominal pain upper, constipation, diarrhea, dyspepsia, flatulence, gastroesophageal reflux disease, gastrointestinal haemorrhage, intra-abdominal haemorrhage, nausea and vomiting.

Nervous system disorders (about 19%), including headache, dizziness, hypoaesthesia, somnolence.

General disorders and administration site conditions (about 16%), including cannula site reaction, fatigue, implant site haemorrhage, injection site thrombosis, infusion site oedema, lethargy, malaise, oedema, oedema peripheral, and pyrexia

The patient population exposed to reparixin oral tablets consists of 111 female receiving either single agent reparixin (REP0210, operable breast cancer: 20 patients) or the combination of reparixin and weekly paclitaxel in metastatic breast cancer (REP0111, phase 1b: 30 patients; REP0114, randomized phase 2: 61 patients).

In the studies completed so far, reparixin was generally well tolerated at all doses studied. Overall, 505 ADRs were reported in 78 patients in the safety population.

70.9% of the ADRs were grade 1 (mild), 22.9% were grade 2 (moderate) and 4.3% were grade 3 (severe). One grade 4 ADR was reported overall (REP0114). In addition, one patient in clinical trial REP0114 experienced serious ADRs including grade 4 peritonitis and grade 5 intestinal perforation.

The most frequent (>10%) ADRs observed in the three studies were:

Gastrointestinal disorders (31.8%), including nausea, vomiting, abdominal pain, discomfort or distension, dyspepsia, flatulence, constipation.

General disorders and administration site conditions (16.4%), including fatigue and peripheral oedema.

# **10.2** Study documentation and record keeping

The investigator should ensure the accuracy, completeness, legibility, and timeliness of the data reported to the sponsor in the source documents and in all required reports.

The investigator must keep source documents for each subject in the study.

The investigator and the sponsor should maintain the study documents as specified in the "Essential Documents for the Conduct of a Clinical Trial" chapter 8 of ICH-GCP and as required by the applicable regulatory requirement(s).

These are documents which individually and collectively permit evaluation of a study and the quality of the data produced and include groups of documents, generated before the study commences, during the clinical study, and after termination of the study and include but are not limited to, study protocol, amendments, submission and approval of Ethics Committee (EC), raw data of subjects, insurance contracts, certificate of analysis of the IMP(s), drug accountability records, signed informed consent forms, confidential subjects identification code.

The investigator and the sponsor should take measures to prevent accidental or premature destruction of these documents.

Study documents must be retained by the investigator and the sponsor as long as needed to comply with ICH-GCP, national and international regulations. By signing the protocol, the investigator and the sponsor agree to adhere to these requirements.

# 10.3 Ethical considerations, quality assurance and monitoring

The procedures outlined in this clinical trial protocol are designed to ensure that the Sponsor and the Investigators from the Clinical Sites perform their activities throughout the set-up, conduct, evaluation, documentation and analysis of the study, in accordance to the principles of the Good Clinical Practice (GCP) guidelines of the International Conference on Harmonization (ICH) and the Declaration of Helsinki. The study will be carried out adhering to local legal requirements and the applicable national laws, whichever represents the greater protection for the individuals.

Study protocol, patient information and informed consent will be submitted to the appropriate Ethics Committee for approval. The Sponsor will be responsible to inform in a timely manner the appropriate Ethics Committee about any changes in the study protocol which could interfere with the patient's safety.

Due to the constrains and risks of the ongoing COVID-19 pandemia, no on-site monitoring activities will be carried out. Remote monitoring will be available periodically or at the investigators' request via web or phone communications with the adequate Sponsor personnel or their approved representatives.

# 10.4 Informed consent

The investigators or sub-investigators involved in this clinical trial who are responsible for treating the hospitalized patient for COVID-19 are responsible for providing all necessary information about the participation in the study to their patients, and consequently to obtain the written Informed Consent. The same procedure applies to the information of the patient and providing of consent to the processing of personal data according to the European Regulation n. 679/2016 on the Protection of Personal Data, the Personal Data Protection Code (Legislative Decree 196/03) and subsequent amendments and additions, and to the provisions, guidelines and general authorizations of the National Guarantor for personal Data Protection.

# 10.5 Data collection

The investigator must ensure that the clinical data required by the study protocol are carefully reported in the subject's source documents detailing the unique identification number and the date and time of the study procedures performed. Any correction to the source data entries must be carried out by the investigator or a designated member of staff. Incorrect entries must not be covered with correcting fluid, or obliterated, or made illegible in any way. A single stroke must be drawn through the original entry. Corrections have to be dated and initialled. The investigator must provide a reasonable explanation for all missing data. The source documents will be completed, signed by the investigator, the sensitive data will be obscured (i.e. only randomization number will be clearly legible) and the source document will be made available to the Sponsor for data management procedures.

# 10.6 Confidentiality and data protection

By signing this protocol, the investigator agrees to keep all the information provided by the sponsor in strict confidentiality and to request the same confidentiality from his/her staff. Study documents provided by the sponsor (protocols, randomization list and other materials) will be stored appropriately to ensure confidentiality. The information provided by the sponsor to the investigator cannot be disclosed to others without direct written authorisation from the sponsor, except for the extent necessary to obtain the informed consent from the subjects wishing to participate in the study.

Data on subjects collected in the source documents during the study will be transferred to the Sponsor in an anonymized way. If, as an exception, for safety or regulatory reasons identification of a subject becomes necessary, the sponsor and the investigator will be bound to keep this information confidential.

# 10.7 Unique subject identifier

All the subjects who sign the informed consent form for the present study will be coded with "unique subject identifiers". The unique subject identifier consists of the sponsor study code (i.e. REPAVID-19), the 3-digit site number (i.e. 001), the 4-digit screening number (e.g. S001, S002, etc.) and, if applicable, the 3-digit subject randomisation number (e.g. 001, 002, etc.).

Study code, site number, screening number and subject randomisation number are separated by slashes ("/").

## 10.8 Database management

The Sponsor will provide a double data entry with total re-entry of data and discrepancy resolution by a second data entrist and will update and verify the database and create the final data sets.

## **10.9** Coding dictionaries

Medical/surgical history and underlying diseases and AEs will be coded using the Medical Dictionary for Regulatory Activities (MedDRATM). Previous and concomitant medications will be coded using the WHO Drug Dictionary Enhanced (WHODDE). The version of the coding dictionaries will be stated in the study report.

## **10.10** Publication policy

Study results will be communicated in full to the competent Health Authorities by the submission of a complete clinical study report.

The sponsor agrees that the study results may be published by the investigator, and the investigator agrees to submit any manuscript (abstract, publication, paper, etc.) to the sponsor before any public disclosure.

This will be done in order to ensure that clinical study results are reported in an objective, accurate and balanced manner. The sponsor reviews the proposed manuscripts, before submission, within a reasonable period of time (30-90 days in relation with the complexity of the work).

The investigator will also be provided by the sponsor with the clinical study report and the results of any additional analysis, tables, figures, etc. undertaken for the purposes of the article, in order to take responsibility for the content of the publication(s). On an exceptional basis, the sponsor may temporarily delay registration of certain data elements (e.g. compound, name, outcome, measures, etc.) to seek necessary intellectual property protection. This is because early disclosure of such data could, in some circumstances, prevent or negatively impact patentability.

[figure not shown]
# **10.11** Administrative aspects

The investigational medicinal products required for the conduct of this study will be provided free of charge by the Sponsor to the participating clinical sites.

Coverage for any damage resulting from the participation of the subjects in the clinical trial is warrented. In addition to the general insurance of the individual participating clinical centers, an insurance cover will be issued in favour of the subjects participating in this clinical study. The insurance is in compliance with the local regulation and with the requirements of the Health Authorities.

#### **11 TABLES AND FIGURES**

#### 11.1 Study outline ±

Phase 2 study to continue with Phase 3. In fase 3 Reparixin will be offered as rescue medication. Final design of Phase 3 to be adapted based on Phase 2 results.

### **11.2** Schedule of Evaluations

The following schedule reports the relative timeframes and all the evaluations and assessments that are performed during the study:

Study procedures	Screening	Baseline	Day 1	Day 2	Week 1	End of treatment	End of follow up
Informed Consent	Х						-
Inclusion/Exclusion Criteria	X	Х					
Pregnancy Test	X						Х
Randomization		Х					
Demographics	Х						
Medical History	X						
Previous And							
Concomitant	Х	X	Х	Х	Х	Х	Х
Medications							
Clinical severity	X	X	Х	X	X	Х	Х
score	Λ	Λ	Λ	Λ	Λ	Λ	Λ
Liker scale	Х	Х	Х	Х	Х	Х	Х
Dyspnea VAS scale	Х	Х	Х	Х	Х	Х	Х
Body temperature	Х	Х	Х	Х	Х	Х	Х
Hematology	V	X	$\mathbf{v}$	v	X	V	Х
evaluations*	Х	л	Х	X	Λ	Х	Λ
Oxigen treatment	X	X	Х	X	X	Х	Х
(time and quantity)	Λ	Λ	Λ	Λ	Λ	Λ	Λ
Mechanical	Х	X	Х	Х	Х	Х	Х
ventilation (Yes/No)	Λ	Λ	Λ	Λ	Λ	Λ	Λ
ICU admission	Х	X	Х	Х	Х	Х	Х
(Yes/no)	Λ	Λ	Λ	Λ	Λ	Λ	Λ
Chest radiologic	Х	X§	X§	X§	X§	Х	X§
imaging	Λ	$\Lambda^{\circ}$	$\Lambda^{\mathfrak{g}}$	$\Lambda^{\circ}$	$\Lambda^{\circ}$	Λ	$\Lambda^{\circ}$
PaO2, SpO2, FiO2	Х	Х	Х	Х	Х	Х	Х
CRP, Hs-CRP	Х	Х	Х	Х	Х	Х	Х
Cytokine profile **	Х	Х	Х	Х	Х	Х	Х
Reparixin blood			$\mathbf{v}$	v	v	V	V
concentration **			Х	Х	Х	Х	Х
SARS-CoV-2		v			v	V	V
virologic counts **		X			Х	Х	Х
Study drug		X					
dispensation		Λ					
Verify study							
medication dosing			Х	X	Х	Х	
compliance							
Record AEs / SAEs	Х	Х	Х	Х	Х	Х	Х

\* Including routine hematology as for local laboratory procedures and predefined hematochemical evaluations required for this study; \*\* Not mandatory; § When deemed appropriate by the investigators.

#### Appendix 3. Investigator's Brocure (IB)

Please refer to dedicated document

### **Appendix 4. Investigational Drug Labels**

Please refer to dedicated document

**Appendix 5. Severe Adverse Event (SAE) reporting form and compltion guideline** Please refer to dedicated document

**Appendix 6. Pregnancy reporting form and completion guideline** Please refer to dedicated document

**Appendix 7. Informed consent form** Please refer to dedicated document

RTF	Rich Text Format
SAE	Serious Adverse Event
SAF	Safety set
SAP	Statistical Analysis Plan
SARS-CoV-2	Severe Acute Respiratory Syndrome CoronaVirus 2
SAS	Statistical Analysis Systems
SD	Standard Deviation
SE	Standard Error
SI	Standard International
SOC	System Organ Class
TEAE	Treatment Emergent Adverse Event
TESAE	Treatment Emergent Serious Adverse Event
TID	Ter in die - three times a day
TLF(s)	Tables, Listings and Figures
VAS	Visual Analog Scale
WHO DD	World Health Organization Drug Dictionary

Revision History

Document Version	Changes Made	Document Date
Final 1.0	First release	29 November 2020

1. Introduction

This document outlines the statistical methods to be implemented in the analysis of the data of REPAVID-19 Clinical Trial. The purpose of this plan is to provide general guidelines from which the analysis will proceed, containing a more technical and detailed elaboration of the principal features of the analysis described in the protocol. Any changes to the protocol or Case Report Form (CRF) may necessitate updates to the Statistical Analysis Plan (SAP). In case of deviations from this updated SAP, explanations will be provided in the clinical study report.

This SAP is based on study protocol Version n. 1.5 - April 23, 2020¹ and Case Report Form Version 1.0 – April 30, 2020².

2. Study Objectives

The objective of this clinical trial is to assess efficacy and safety of reparixin as compared to the Standard of care in hospitalized adult subjects with severe COVID-19 pneumonia.

3. Study Design

General design and plan

The study is designed as an adaptive, randomized, controlled, multicenter study to evaluate efficacy and safety of reparixin in hospitalized adult subjects with severe COVID-19 pneumonia.

In the phase 2 segment of this study, subjects will be randomized 2:1 to reparixin oral tablets 1200 mg (Group 1, active treatment) or standard of care (Group 2, control arm). In case of worsening (e.g. need of Intensive Care Unit (ICU) and/or mechanical ventilation) after the first 24hrs, subjects will be offered a rescue medication based on their physicians' judgement, without any constrain from the sponsor. The administration of rescue medications is allowed, without constituting a protocol deviation.

In the phase 3 segment of this study, it is planned that subjects will be randomized 2:1 to reparixin or standard of care. In case of worsening after the first 24hrs, subjects under the control arm will be offered a rescue medication with the active treatment (reparixin 1200 mg oral tablets TID) or reparixin 2.772 mg/kg body weight/hour IV infusion, if the oral route is unfeasible for the clinical condition. The phase 3 design will be reassessed and decided based on the results of the phase 2.

3.1 Visit Schedule and Visit Windows

Assessments and study visits will be performed as listed in Table 1. Paragraph no. 7 “Assessments and procedures” of Study Protocol contains additional details about scheduled visits, evaluations and assessments that are performed during the study.

Baseline is defined as the last visit prior to randomization. Unless otherwise specified, baseline values are defined as the measurements taken during this visit.

Table 1: Schedule of evaluations

Study procedures	Screening	Baseline	Day 1	Day 2	Week 1	End of treatment	End of follow up
Informed Consent	X						
Inclusion/Exclusion Criteria	X	X					
Pregnancy Test	X						X
Randomization		X					
Demographics	X						
Medical History	X						
Previous And Concomitant Medications	X	X	X	X	X	X	X
Clinical severity score	X	X	X	X	X	X	X
Liker scale	X	X	X	X	X	X	X
Dyspnea VAS scale	X	X	X	X	X	X	X
Body temperature	X	X	X	X	X	X	X
Hematology evaluations*	X	X	X	X	X	X	X
Oxygen treatment (time and quantity)	X	X	X	X	X	X	X
Mechanical ventilation (Yes/No)	X	X	X	X	X	X	X
ICU admission (Yes/no)	X	X	X	X	X	X	X
Chest radiologic imaging	X	X§	X§	X§	X§	X	X§
PaO ₂ , SpO ₂ , FiO ₂	X	X	X	X	X	X	X
CRP, Hs-CRP	X	X	X	X	X	X	X
Cytokine profile **	X	X	X	X	X	X	X
Reparixin blood concentration **			X	X	X	X	X
SARS-CoV-2 virologic counts **		X			X	X	X
Study drug dispensation		X					
Verify study medication dosing compliance			X	X	X	X	
Record AEs / SAEs	X	X	X	X	X	X	X

* Including routine hematology as for local laboratory procedures and predefined hematochemical evaluations required for this study;

** Not mandatory; § When deemed appropriate by the investigators.

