3.5 Efficacy endpoints

3.5.1 Primary endpoints

- Primary Endpoint for phase 2: Composite endpoint of clinical events (the subject requires at least one of the following: supplemental oxygen requirement, invasive mechanical ventilation use, admission to ICU, and use of a rescue medication for any reason);
- Primary Endpoint for phase 3: Composite endpoint of death and clinical severe events (the subject dies or requires invasive mechanical ventilation use and/or admission to ICU).

3.5.2 Secondary Endpoints:

- Clinical severity score (a seven-category ordinal scale) at any available time point
- Dyspnea severity (Liker categorical scale and VAS continuous scale) at any available time point;
- Changes in body temperature at any available time point;
- Duration and quantity of supplemental oxygen treatment at any available time point;
- Incidence and duration of mechanical ventilation use at any available time point;
- Incidence of ICU admission need at any available time point;
- Lung damage extension changes from baseline (assessed by Chest CT or Rx) at any available time point;
- Change from baseline in lung exudation degree (assessed by Chest CT or Rx) at any available time point;
- PaO₂ at any available time point;
- SpO₂ at any available time point;
- Partial arteriolar oxygen pressure (PaO₂) to fraction of inspiration O₂ (FiO₂) ratio at any available time point;
- CRP at any available time point;
- Hs-CRP at any available time point;

3.5.3 Exploratory Endpoints (not mandatory):

- Cytokine profile at any available time point;

- Concentration of reparixin in serum over time;
- SARS-CoV-2 virologic counts at any available time point.

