7.2.2 Comparison between treatments

Along with the above summary statistics, comparisons between treatments will be performed as detailed in the next sub-sections. Parametric test (i.e. two-sample t-test for continuous variables, Chi-square test for categorical) will be adopted as first choice. In case the required assumptions are not met, the corresponding non-parametric counterpart will be used (i.e. the two-sample Mann–Whitney U test for continuous variables, and the Fisher’s Exact test for the categorical). Normality of continuous data is assessed by Kolmogorov-Smirnov test.

Comparison will be performed at each available time point, where applicable. Any exception will be declared.

7.2.2.1 *Composite endpoint of phase 2 using Oxygen Delivery System Classification*

The composite endpoints will be summarized along with their single component by a binomial response rate at each time point (only the first event will be considered). The Clopper-Pearson method will be used to estimate the two-sided 95% CIs.

Time to composite endpoint(s) will be performed using the KM methodology and the one-sided log-rank test will be used to test for differences between treatment groups.

7.2.2.2 *Changes in clinical severity score*

Number and proportion along with the 95% confidence interval (Clopper-Pearson’s formula) of subjects with a clinical severity score improvement of at least two points compared to randomization or live discharge from the hospital will be calculated and compared.

7.2.2.3 *Dyspnea severity (Liker scale and VAS scale)*

The comparison of the Liker scale between the two study treatment arms will be performed by means of Wilcoxon signed-rank test, given its ordinal nature.

Number and proportion along with the 95% confidence interval (Clopper-Pearson’s formula) of subjects with

any improvement (improved vs not-improved) will be calculated and compared.

VAS scale comparison between treatments will be performed according to its continuous nature.

7.2.2.4 *Changes in body temperature*

Comparison between treatments in change from baseline of the body temperature will be performed according to the continuous nature of the variable.

7.2.2.5 *Incidence of supplemental oxygen treatment*

Number and proportion along with the 95% confidence interval (Clopper-Pearson's formula) of subjects who worsened according to PaO₂/FiO₂ and to Oxygen Delivery System Classification based on oxygen support will be calculated and compared.

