At each time point the number and proportion of patients within each class (Severe, Moderate, or Mild for PaO₂/FiO₂; Invasive, High Flow, or Low Flow for the type of support) will be provided.

Finally, summary of cumulative quantity (L) and cumulative duration (hours) of oxygen treatment will be performed at 7 days and subsequent time points considering the variable as continuous.

7.2.2.6 *Incidence and duration of mechanical ventilation use*

Number and proportion along with the 95% confidence interval (Clopper-Pearson's formula) of subjects requiring mechanical ventilation will be calculated and compared.

Comparison between treatments in cumulative duration (hours) of mechanical ventilation will be performed at 7 days and subsequent time points considering the variable as continuous. Analysis will be performed overall and stratified by Invasive/Non-invasive mechanical ventilation.

7.2.2.7 *Incidence of ICU admission need*

Number and proportion along with the 95% confidence interval (Clopper-Pearson's formula) of subjects requiring ICU admission will be calculated and compared.

Comparison between treatments in duration (days) of ICU stay will be performed considering the variable as continuous.

7.2.2.8 *Change from baseline in lung damage extension and lung exudation degree (assessed by Chest CT or Rx)*

The comparison of the clinical evaluation of lung damage extension and lung exudation between the two study treatment arms will be performed by means of Wilcoxon signed-rank test.

7.2.2.9 *Respiratory parameters*

Change from baseline of FiO₂, Respiration rate, PaO₂, SpO₂ and PaO₂/FiO₂ will be compared between treatments considering the continuous nature of these variables.

7.2.2.10 *CRP and Hs-CRP*

CRP (mg/L) and Hs-CRP (mg/L) will be compared between treatments considering their continuous nature.

7.3 **Analysis of exploratory efficacy endpoints**

Explorative endpoints (section 3.5.3) will be analyzed at each available time points by means of descriptive statistics. Specifically, analyses will be provided for baseline visit, each post-baseline visit, and the change from baseline measurements to each visit. Comparison between treatments will be performed by means of two-sample t-test or, if assumptions of normality is not confirmed (by Kolmogorov-Smirnov test), two-sample Mann-Whitney U test.

In case of different units of measure considered for the same laboratory parameter, all values will be converted

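### The imaging baseline is tied to a visit where chest imaging is optional, and lung-damage change is tested between arms at four further visits where unblinded investigators choose whom to image

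*SAP*

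**What the plan says.** The schedule in SAP 3.1 (Table 1) repeats protocol 11.2. In the row "Chest radiologic imaging", Screening and End of treatment carry a plain mark. Baseline, Day 1, Day 2, Week 1 and End of follow up carry a footnoted mark meaning "When deemed appropriate by the investigators". No other row has that footnote.

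The baseline rule is general: "Baseline is defined as the last visit prior to randomization. Unless otherwise specified, baseline values are defined as the measurements taken during this visit". Neither SAP 7.2.2.8 nor the derivation rules in SAP Table 7 specify anything else for imaging.

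SAP 3.5.2 lists as a secondary endpoint "Lung damage extension changes from baseline (assessed by Chest CT or Rx) at any available time point", with a matching endpoint for lung exudation. SAP 7.2.2.8 compares the arms on both by a Wilcoxon test. The rule for timing in SAP 7.2.2 is "Comparison will be performed at each available time point, where applicable", followed by a statement that exceptions will be disclosed. SAP 4.8 works from non-missing values.

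SAP 3.3 describes the trial as open-label. Protocol 7.2 leaves imaging to local site procedures, and either CT or X-ray may be used. Protocol 5.2 makes chest imaging an inclusion criterion.

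**The concern.** The general baseline rule suits measures that are required at every visit, such as the severity score, blood gases and CRP. For imaging it points to a visit where there may be no image. A patient whose only pre-randomization image is the required Screening one would then have no baseline, and so no change value even at End of treatment.

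The second problem is who contributes to the tests. At the optional post-baseline visits the imaged patients are those whom a physician who knows the treatment chose to image. If that choice depends on the patient's course differently in the two arms, randomization no longer protects the comparison, and a difference in imaging practice can look like a drug effect in either direction.

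A smaller gap is that nothing says how a CT at one visit and an X-ray at another are to be compared.

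**Working it through.** The plan states no figure for imaging coverage or power, so there is none to reproduce. The check is a count from the schedule, a tracing of the baseline rule, and two illustrations on stated assumptions.

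**1. Coverage (SAP Table 1).** Seven imaging cells: 2 required, 5 optional. After baseline there are five visits: 1 required (End of treatment), 4 optional (Day 1, Day 2, Week 1, End of follow up). Two imaging endpoints at five visits give up to 2 × 5 = 10 between-arm tests, of which 2 × 4 = 8 are on investigator-selected patients.

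**2. Baseline rule.** The rule is "Baseline is defined as the last visit prior to randomization", and "baseline values are defined as the measurements taken during this visit". The schedule has a column named Baseline, and its imaging cell is optional. No text sends the analyst back to Screening when that cell is empty.

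**3. Precision if the Screening image is not used.** Phase 2 has 48 patients at 2:1, so 32 and 16. Let q be the assumed share imaged at the Baseline visit, with End of treatment imaging complete and loss at random. The usable pairs are 32q and 16q. For an assumed standardized effect of 0.9, two-sided 0.05, normal approximation:

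power = Φ(0.9 × √[(32q × 16q)/(48q)] − 1.96) = Φ(2.94√q − 1.96)

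| q | Pairs (reparixin / control) | Power |
|---|---|---|
| 1.0 | 32 / 16 | 0.84 |
| 0.6 | about 19 / 10 | 0.62 |
| 0.2 | about 6 / 3 | 0.26 |

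**4. Selection at optional visits, with no drug effect.**

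*Worked example (all rates assumed).* In both arms 40% have worsened and 80% of worsened patients are imaged. Of stable patients, 20% of controls and 50% of reparixin patients are imaged. The share worsened among those imaged is:

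- Control: 0.4 × 0.8 / (0.4 × 0.8 + 0.6 × 0.2) = 0.32/0.44 = 0.73
- Reparixin: 0.4 × 0.8 / (0.4 × 0.8 + 0.6 × 0.5) = 0.32/0.62 = 0.52

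This is a spurious benefit of 21 points. Exchanging the 20% and 50% gives a spurious harm of the same size.

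*Simulation.* 32 versus 16 patients with the same normal distribution of change; probability of imaging logistic in that change; two-sided Mann-Whitney test at 0.05; 5,000 runs per pattern.

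| Slope per SD (reparixin, control) | Type I error | Mean difference (SD) |
|---|---|---|
| 0, 0 | 0.048 | 0.00 |
| 1, 1 | 0.042 | 0.01 |
| 0, 1 | 0.14 | −0.42 |
| 0, 2 | 0.26 | −0.61 |
| −1, 1 | 0.45 | −0.82 |

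Outcome-related imaging that works the same way in both arms does not inflate the error rate. Inflation appears only when selection differs by arm.

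**The case against.** The strongest reply is that the SAP need not be read this way. Randomization sits in the Baseline column of Table 1, so the last visit before it could literally be Screening, where imaging is required. SAP 7.2.2.8 tests a clinical evaluation of the images. The CRF, which is not among the documents, may record a reader's judgement of change, so that no numeric baseline is subtracted. The testing rule is qualified by applicability, and exceptions are to be disclosed. SAP 4.1 and 4.8 already provide for the number of observations and a missing category, so much of the imaging coverage would be visible.

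All of this stands as a limit on certainty. It does not remove the point. If Screening was meant, imaging is the one scheduled measure where the difference matters and the SAP does not say so. If a reader judges change, the SAP does not say against which image. The applicability clause names no restriction for imaging. Visible counts reveal selection but do not correct the p-values.

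Two objections to possible remedies are also right. Dropping pairs with one CT and one X-ray could remove the patients who worsen and change modality, which is informative exclusion in a trial of 48. And End of treatment is not a common time point: protocol sections 1 and 6.1 allow reparixin to be prolonged from 7 up to 21 days in case of improvement, and no corresponding end-of-treatment day is defined for standard of care.

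**Conclusion.** The point holds. Followed on their natural reading, the stated rules can set aside the required pre-randomization image and will test subsets chosen by unblinded physicians at four of five post-baseline visits.

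A reader might infer more than this, and the documents do not support it:

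- *That the Screening image is certainly lost.* The baseline definition is ambiguous and the form of the change variable is not visible.
- *That the optional-visit tests are known to be biased, or biased toward reparixin.* Bias needs selection that differs by arm. The open label permits that, but no imaging rates are given, and either direction is possible. The figures of 21 points and 0.14 to 0.45 illustrate assumed patterns and are not estimates.
- *That the trial's conclusion is at risk.* These are secondary endpoints. The phase 2 composite in SAP Table 7 uses no imaging, and SAP 7.1.3.1 bases the decision on phase 3 on the primary analysis alone.

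The correction is worth making because it is specific and nearly free, and because SAP Table 6 lets phase 2 results inform the choice of phase 3 endpoints.

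**What to change.** - **SAP 3.1 or Table 7:** define the imaging baseline as the last image on or before randomization, whether from Screening or Baseline.
- **SAP 7.2.2.8:** limit the inferential between-arm comparison to End of treatment, the only required post-baseline image. State that its timing varies by patient and can depend on response, so the result is read with that caution.
- **Optional visits:** report them descriptively, with the number imaged per arm at each visit.
- **Modality:** keep mixed pairs in the main analysis. Report the numbers of CT-CT, X-ray-X-ray and mixed pairs by arm. If the CRF records modality, add a same-modality sensitivity analysis.

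Cost: a change of SAP wording, with no new visit or procedure. The p-values at the optional visits are given up. The modality items depend on what the CRF captured, which the documents do not show.
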